5.1. Analysis of outcomes

5.1.1. Primary outcome

Assessment of the safety of C19-A3 GNP administration in terms of adverse events at the dose used is the primary outcome. This includes general safety concerns, induction of hypersensitivity and exacerbation of β -cell specific autoimmunity with accelerated β -cell loss. All enrolled patients will be included in the following analysis.

General Safety

To address general safety concerns at screening and 0, 4, 8 and 14 weeks a physical examination will be conducted. A review of AEs will be performed at all visits according to seriousness, causality and expectedness. Types of AEs, body systems involved and outcomes of the AE will be categorised and analysed by incidence per person dose used. All AEs will be collated

Hypersensitivity

Patients will be observed for local and systemic reactions post injection. Number of local reactions will be analysed by incidence per person dose used, size of the erythema note and time taken for erythema note size to be reduced to < 1 cm will be analysed by mean and standard deviation. Systemic reactions will be analysed by incidence per person dose used. Therapies used and outcome will be counted and reported.

Exacerbation of β -cell specific autoimmunity with accelerated β -cell loss

Differences between week 0 and 14 will be calculated for each patient and summarised by mean and standard deviations for the following parameters:

- Measurement of islet cell autoantibodies (against insulin, GAD-65, IA-2 and ZnT8)
- Measurement of pro-inflammatory β -cell specific T cell responses (analytes to be defined)

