5.1.2. Secondary outcomes

Differences in the parameters set below will be calculated for each patient and summarised by mean and standard deviations. Potential differences between patients receiving treatment within and outside treatment schedule will also be explored, if required.

- T cell responses to C19-A3 GNP as determined by changes from baseline of interferon gamma and IL-10 ELISPOT responses to this peptide in blood following treatment at weeks 0, 9 and 14.
- T cell responses to C19-A3 GNP as determined by changes from baseline of interferon gamma and IL-10 ELISPOT responses to this peptide in

draining axillary lymph node before treatment and following the last treatment administration (four aspirations: before and after visit 1 and visit 3)

- Changes in additional immunological biomarkers (e.g. flow cytometry profiles, T reg assays, autoantibodies, beta cell and T cell free DNA markers) from baseline at week 0, 9 and 14.
- Effects on residual insulin requirement and c-peptide secretion at week 14 as compared to baseline as assessed by secreted C peptide AUC after a mixed meal tolerance test and a stimulated urine c-peptide test.
- Effects on glycaemic control assessed by blood sugar profiles and HbA1c at week 14 as compared to baseline
- Scores on quality of life and diabetes self-management (week 0 and week 14).

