5.3.2 Safety urinalysis

Urinalysis for pH blood, protein, urine beta-2-microglobulin and albumin/creatinine ratio will be done at screening and visits 1, 2, 4, 5 and 6 and urine for cystatin-c will be collected at visits 1, 4, 5 & 6. A urine pregnancy test will be completed on females only, at all trial visits. Frequency of abnormal urine PH blood and protein per patient over time and positive pregnancy tests will be enumerated.

In addition to the final report, interim safety reports will be circulated to DSMB for review after the sentinel patient and the 4th patient receiving his/her first injection.

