5.3.3 Gold concentration

At visits 1, 1b, 3b, 4, 5 and 6 blood and urine samples will be taken for gold concentrations to enable assessment of gold excretion. Laboratory measurements for these will be performed at the LGC laboratory, Cambridgeshire. Concentration of gold for each patient over time will be analysed by half-life of elimination at the end of the study.

The major organ of accumulation and excretion of the gold nanoparticles is the kidney. Safety reports on markers of kidney function in blood (levels of electrolytes, urea, creatinine, calcium, phosphate, and magnesium) and urine (blood in urine, protein in urine, cystatin-c and beta-2-microglobulin) have already been covered in 5.3.1 and 5.3.2.

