¹List reason for not performing ECG by subject and visit no in a separate spreadsheet. ²List reasons for not completing physical examination by subject and visit no in a separate spreadsheet. ³List all information about the abnormalities as captured in CRF by patient and visit no in a separate spreadsheet. ⁴List all clinically significant abnormalities as captured in CRF by patient and visit no in a separate spreadsheet. ⁵List changes in insulin as captured in the change of insulin log by patient in a separate spreadsheet. ⁶List concomitant medications as captured in concomitant medication log by patient in a separate spreadsheet. ⁷List reaction details as captured in post injection skin reaction log by patient and visit no in a separate spreadsheet. ⁸List whether the observation was judged to be clinically significant and whether it is an AE.

- Endpoints Analysis (laboratory assays)

Table 6 shows the headings of the data file for endpoints assessment with laboratory assays

For each of the analytes: eg GAD65

| | | | | |
|--------------|-----------|--------------|----------|----------|
| Screening No | Centre No | Treatment No | Visit -2 | Visit -1 |
|--------------|-----------|--------------|----------|----------|

Cont'd

| | | | | | |
|---------|---------|---------|---------|---------|---------|
| Visit 1 | Visit 2 | Visit 3 | Visit 4 | Visit 5 | Visit 6 |
|---------|---------|---------|---------|---------|---------|

For a full list of all the analytes, please refer to the Data Transferral Plan in Section 10 of the Data Management Plan

- Questionnaire Data

Table 7 shows the headings of the data file for endpoints assessment with questionnaire data

At Visit 1

| | | | | | | |
|--------------|-----------|----------|-------|------------|---------------|--------------|
| Screening No | Centre No | Visit No | Rx No | HFS items* | ADDQoL items* | DTSQs items* |
|--------------|-----------|----------|-------|------------|---------------|--------------|

Multiple columns

At Visit 5

| | | | | | | | |
|--------------|-----------|----------|-------|------------|---------------|--------------|--------------|
| Screening No | Centre No | Visit No | Rx No | HFS items* | ADDQoL items* | DTSQs items* | DTSQc items* |
|--------------|-----------|----------|-------|------------|---------------|--------------|--------------|

Multiple columns

- Safety data

Table 8 shows the headings of the data file for AE assessment

| | | | | | | | |

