|--------------|-----------|-------|-------|------------|----------|-----------------------|---------------------------|
| Screening No | Centre No | Rx No | AE no | Start date | End date | Serious? 1=Y / 2=N | If Y, print full SAE form |
|--------------|-----------|-------|-------|------------|----------|-----------------------|---------------------------|

Cont'd

| | | | |
|---|--|---|---|
| Severity 0=no AE, 1=mild, 2=moderate,3=severe | Study drug action 0=none 1=temp interrupt 2=permanently withdraw | Outcome 0=resolved 1=resolved with sequela 2=not resolved | Relationship to study drug 0=not related 1=unlikely 2=possibly 3=probably 4=very likely |
|---|--|---|---|

Table 9 shows the headings of the data file for safety blood test reporting

| | | | | | | |
|--------------|-----------|----------|-------------------------|---------------------------|------------------|------------------|
| Screening No | Centre No | Visit No | Hb (Males) Normal (Y/N) | Hb (Females) Normal (Y/N) | Hct Normal (Y/N) | MCV Normal (Y/N) |
|--------------|-----------|----------|-------------------------|---------------------------|------------------|------------------|

Cont'd

| | | | | | | |
|------------------|------------------|------------------|------------------------|--------------------------|------------------------|--------------------------|
| MCH Normal (Y/N) | WBC Normal (Y/N) | RBC Normal (Y/N) | Platelets Normal (Y/N) | Neutrophils Normal (Y/N) | Basophils Normal (Y/N) | Eosinophils Normal (Y/N) |
|------------------|------------------|------------------|------------------------|--------------------------|------------------------|--------------------------|

Cont'd

| | | | | | | |
|-------------------------------|--------------------|----------------------|-------------------------|------------------------|-------------------|---------------------|
| Prothrombin Time Normal (Y/N) | HbA1c Normal (Y/N) | Glucose Normal (Y/N) | Creatinine Normal (Y/N) | Potassium Normal (Y/N) | Urea Normal (Y/N) | Sodium Normal (Y/N) |
|-------------------------------|--------------------|----------------------|-------------------------|------------------------|-------------------|---------------------|

Cont'd

| | | | | | | |
|----------------------|------------------------|------------------------|-----------------------------------|----------------------------|----------------------|------------------------------|

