| Calcium Normal (Y/N) | Phosphate Normal (Y/N) | Magnesium Normal (Y/N) | Alkaline Phosphatase Normal (Y/N) | Total Protein Normal (Y/N) | Albumin Normal (Y/N) | Total Bilirubin Normal (Y/N) |
|----------------------|------------------------|------------------------|-----------------------------------|----------------------------|----------------------|------------------------------|

Cont'd

| | | | | | | |
|-------------------------|-------------------------|------------------|--------------------------------|-------------------|-------------------|----------------------------|
| AST (SGOT) Normal (Y/N) | ALT (SGPT) Normal (Y/N) | TSH Normal (Y/N) | Total Cholesterol Normal (Y/N) | HDLC Normal (Y/N) | LDLC Normal (Y/N) | Triglycerides Normal (Y/N) |
|-------------------------|-------------------------|------------------|--------------------------------|-------------------|-------------------|----------------------------|

Cont'd

| | | |
|------------------|------------------|------------------|
| IgA Normal (Y/N) | IgM Normal (Y/N) | IgG Normal (Y/N) |
|------------------|------------------|------------------|

List details as captured in CRF for parameter not within the normal range for the patient, visit and parameter concerned

Table 10 shows the headings of the data file for safety urine test reporting

| | | | | | |
|--------------|-----------|----------|------------------------|-----------------------|-----------------------------|
| Screening No | Centre No | Visit No | PH Blood Normal (Y/N)* | Protein Normal (Y/N)* | Pregnancy test (+ve, -ve)** |
|--------------|-----------|----------|------------------------|-----------------------|-----------------------------|

* List details as captured in CRF for parameter not within the normal range for the patient, visit and parameter concerned

**Please flag patients with positive pregnancy test

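### The SAP says cystatin-c and beta-2-microglobulin are already covered, but it plans no analysis of either, and within-range creatinine change could go unreported

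*SAP*

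**What the plan says.** SAP 5.3.3, after describing the gold concentration analysis, notes that the kidney is the main organ of accumulation and excretion. It then says that safety reports on the renal markers in blood and urine are dealt with elsewhere: "blood in urine, protein in urine, cystatin-c and beta-2-microglobulin) have already been covered in 5.3.1 and 5.3.2".

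Section 5.3.1 lists the safety blood tests, including urea and creatinine, and plans a count of abnormal results per patient over time. Section 5.3.2 gives the collection visits for beta-2-microglobulin, albumin/creatinine ratio (ACR) and cystatin-c. Its only analysis sentence is "Frequency of abnormal urine PH blood and protein per patient over time and positive pregnancy tests will be enumerated".

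The data files in Appendix 2 match. The result columns of Table 10 are "PH Blood Normal (Y/N)* | Protein Normal (Y/N)* | Pregnancy test (+ve, -ve"). In Table 9 the creatinine column is "Creatinine Normal (Y/N"), and urea is coded the same way. The rule for further detail is "List details as captured in CRF for parameter not within the normal range for the patient, visit and parameter concerned".

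Protocol 10.1 gives the reason for the markers: the kidney was the most exposed vital organ in the pre-clinical studies, collecting on average 30% of the dose in rats. It also reports no toxicity at up to 500 times the intended dose.

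**The concern.** A cross-reference that says something is covered stops a programmer or report writer from looking further. Here it leads to sections that describe collecting the samples but not analysing them. Followed literally, the final report could contain no post-dose result for two of the markers chosen to watch the organ of most concern.

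The Y/N coding of creatinine adds to this. Raised creatinine at entry is an exclusion, so every patient should start as normal. A new out-of-range value would be counted and listed. A rise that stays inside the range would not.

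This is an uncontrolled first-in-man study of 8 patients with safety as the primary endpoint. There is no comparison group, so each patient's change from his or her own pre-dose value is the main renal evidence available.

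**Working it through.** **Step 1. Follow the cross-reference, marker by marker.**

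| Marker | Named in 5.3.1 | Collected under 5.3.2 | In the 5.3.2 analysis sentence | Column in Table 9 or 10 | Named in 5.1.1 or 5.1.2 |
|---|---|---|---|---|---|
| Cystatin-c | No | Visits 1, 4, 5, 6 | No | None | No |
| Beta-2-microglobulin | No | Screening, visits 1, 2, 4, 5, 6 | No | None | No |
| ACR | No | Screening, visits 1, 2, 4, 5, 6 | No | None | No |
| Creatinine | Yes, abnormal count | Not applicable | Not applicable | Y/N (Table 9) | No |

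ACR is not in the 5.3.3 sentence, but it has the same gap. The analysis sentence in 5.3.2 and the columns of Table 10 agree with each other, so a column lost in text extraction is unlikely.

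**Step 2. Look for another route to an analysis.**

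- Table 3 holds ACR and beta-2-microglobulin, but only as baseline characteristics.
- Table 6 is a per-visit laboratory file that may hold these analytes. Its contents are deferred: "For a full list of all the analytes, please refer to the Data Transferral Plan in Section 10 of the Data Management Plan". That plan is not among the documents. Table 6 is in any case a file layout with no summary attached.
- SAP 5.1.1 plans per-patient changes ("Differences between week 0 and 14 will be calculated for each patient and summarised by mean and standard deviations for the following parameters"), and 5.1.2 does likewise ("Differences in the parameters set below will be calculated for each patient and summarised by mean and standard deviations"). Neither list includes a renal marker.
- Protocol 15.1 plans comparisons with baseline in general terms and names no variable.

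**Step 3. Count the post-dose results with no named summary (8 patients, complete data, visits in SAP 5.3.2).**

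- Beta-2-microglobulin: visits 2, 4, 5, 6 = 4 per patient; 8 × 4 = 32.
- Cystatin-c: visits 4, 5, 6 = 3 per patient; 8 × 3 = 24.
- Together: 32 + 24 = 56.
- ACR: visits 2, 4, 5, 6 = 4 per patient; 8 × 4 = 32. With ACR: 56 + 32 = 88.

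**Step 4. Find how large a creatinine rise a Y/N code can hide.** The documents give no reference range. Assume the upper limit is r times the lower limit, with r from 1.5 to 2.0. The largest rise that stays coded normal is:

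| Starting value | Formula | r = 1.5 | r = 2.0 |
|---|---|---|---|
| Mid-range | (r − 1)/(r + 1) | 0.5/2.5 = 20% | 1/3 = 33% |
| A quarter of the way up | r/(1 + 0.25(r − 1)) − 1 | 1.5/1.125 − 1 = 33% | 2/1.25 − 1 = 60% |
| Lower limit | r − 1 | 50% | 100% |

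**Step 5. Check two inconsistencies that affect the fix.**

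- *Cystatin-c sample type.* It is serum in Table 1 of both documents and in protocol Figure 3, but urine in protocol 6.7 and 10.1 and in SAP 5.3.2 and 5.3.3. Until this is settled, it is unclear whether a column belongs in Table 9 or Table 10.
- *Visit 1 safety bloods.* They are marked in Table 1 of both documents but absent from protocol Figure 3, protocol 10.1 and SAP 5.3.1. Figure 3 totals 10 + 25 + 1 + 64 + 2 = 102 ml at visit 1 and 11 + 10 + 25 + 1 + 64 + 2 = 113 ml at visit 5. The 11 ml difference is the safety draw. This decides which creatinine value serves as baseline.

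**The case against.** The strongest points on the other side are these.

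- *Protein might include cystatin-c.* Protocol 10.1 puts cystatin-c in brackets after protein when it lists the urinalysis. On that wording, the protein count in SAP 5.3.2 could be said to include it. But SAP 5.3.3 lists protein in urine and cystatin-c as separate items, and 5.3.2 gives them different visits. Beta-2-microglobulin is uncovered on either reading. The bracket is one more wording to reconcile.
- *A Y/N column does not prove that numeric values are missing.* Table 9 also codes HbA1c as Y/N, yet SAP 5.1.2 analyses its change from baseline. This stands: numeric renal values may sit in the Table 6 file, and new columns may then be unnecessary. It does not supply the missing analysis.
- *Creatinine does have a stated analysis.* Counting abnormal values fits the simple descriptive statistics planned for an unpowered study, and no document promises within-range trends. This is fair. For creatinine the point is a limitation of the method, not a false statement in the SAP, and the percentages in Step 4 would apply to any analyte with such a range.
- *Other safeguards exist.* Out-of-range bloods, abnormal urine blood or protein and adverse events are still reported. Safety bloods are reviewed at follow-up visits. The Data Safety Monitoring Board receives reports after the sentinel patient, after the fourth patient's first injection, and at the end. These reduce the risk of missing a gross event, but none specifies a summary of the two markers.

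**Conclusion.** The concern holds. SAP 5.3.3 is wrong as written for cystatin-c and beta-2-microglobulin: 5.3.2 covers their collection only, and no other part of the SAP plans an on-treatment analysis. The gap is 56 post-dose results with no named summary, or 88 with ACR, assuming 8 patients with complete data.

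For creatinine, a rise of 20-33% from mid-range, and up to 50-100% from the lower limit, could go unreported. Those figures rest on the assumed ratio of 1.5 to 2.0 between the reference limits.

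This is a reporting gap, not evidence of renal harm, and it should be fixed before analysis. Confidence is high that the analysis is missing. Whether numeric values are already in the Table 6 file cannot be determined from these documents.

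**What to change.** - Replace the cross-reference in SAP 5.3.3 with a stated analysis. For creatinine, cystatin-c, urine beta-2-microglobulin and ACR, report each patient's value at every visit and the change from the last pre-dose value at every post-dose visit, as a listing or profile plot. Keep the counts of abnormal results alongside.
- Supply numeric values for these four markers. Either add columns to Tables 9 and 10 or, if Table 6 already carries the analytes, name them there and cite Table 6 in 5.3.
- Reconcile the cystatin-c sample type across Table 1, Figure 3, protocol 6.7 and 10.1 (including the bracketed wording) and SAP 5.3.2 and 5.3.3.
- Reconcile whether safety bloods are drawn at visit 1. Until then, use the last available pre-dose value as the creatinine baseline.

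The cost is SAP wording plus a few columns or one cross-reference, and possibly a small protocol correction for the two inconsistencies. Cystatin-c, beta-2-microglobulin and ACR are already scheduled at visit 1 and follow-up, so they need no new sampling. The drawback is one extra table or plot, which in 8 patients will show some chance fluctuations that need clinical comment.

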5.3.4 Pregnancy outcome

If a patient or their partner got pregnant during the study or within 85 days of receiving the final injection, they will be followed up until child birth. Pregnancy outcomes will be enumerated at the end of the follow up. A final safety report will be provided to DSMB for review.

6. Presentation of Data for Analysis

- The trial manager working in conjunction with the data manager and consult the trial statistician if required should ensure all data presented to the trial statistician are clean and validated.
- The study database should be frozen by the data manager or the person responsible for the data.
- The statistician/designee should work on a copy of the study database that has been downloaded for them by the data manager.
- Any amendments to the study database should be documented and a new version supplied to the statistician.
- Presentation of data depends on purpose of the analysis and the method of data capture. For detailed specification of data for analysis, please see Appendix 2.

7. Statistical Software

Analysis will be carried out using SPSS version 22 or later.

8. Amendments

Amendments of the SAP will be circulated to DSMB for review and ratification.

Appendix 1

Table (i) Baseline Characteristics of the enrolled and not enrolled

| Mean (\pmSD) or N (%) | Enrolled | Screened but not enrolled |
|--|-----------------|----------------------------------|
| Age (years) Range | | |
| Female (%) | | |
| Ethnicity White (%) Mixed race(%) Asian (%) Black (%) Chinese (%) Others (%) | | |
| Body mass index | | |
| Age of diagnosis | | |
| Duration of diabetes | | |

Table (ii) Adherence to intervention

| N (%) | Visit 1 | Visit 2 | Visit 3 | Visit 4 | Visit 5 | Visit 6 |
|----------------------------------|----------------|----------------|----------------|----------------|----------------|----------------|
| On target (Within window) | | | | | | |
| Protocol Violations / Deviations | | | | | | |
| Missed dose/ followup | | | | | | |

The following tables summarised formats of data files required for the current study according to the purpose of analysis (and method of data capture where appropriate)

- Eligibility assessment

Table 1 shows the headings of the data file for eligibility assessment

| | | | |
|--------------|-----------|----------------------------------|--------------------------------------|
| Screening No | Centre No | Satisfy screening criteria (Y/N) | If N, additional report ¹ |
|--------------|-----------|----------------------------------|--------------------------------------|

¹List all reasons of failure for each screened subject as captured in CRF in a separate spreadsheet.

- Description of baseline characteristics (demographical and clinical data)

Table 2 shows the headings of the data file to describe baseline characteristics with demographic and clinical data

| | | | | | | |
|--------------|-----------|-----|-----|--------------------------------|-------------------|---------------------------------|
| Screening No | Centre No | DOB | Sex | Date of assessment at Visit -2 | Date of diagnosis | Date of 1 st insulin |
|--------------|-----------|-----|-----|--------------------------------|-------------------|---------------------------------|

Cont'd

| | | | | | |
|-----------------------|--------------------------------------|-------------------|---------------------------|----------------------|--------------------------------------|
| Ongoing med plm (Y/N) | If Y, additional report ¹ | Ever smoked (Y/N) | If Y, duration of smoking | Current smoker (Y/N) | If Y, additional report ² |
|-----------------------|--------------------------------------|-------------------|---------------------------|----------------------|--------------------------------------|

Cont'd

| | | | | |
|---------------------|--------------------------------------|-----------------------------|-----------------------|----------------------------------|
| Former smoker (Y/N) | If Y, additional report ³ | Recreational drug use (Y/N) | Consume alcohol (Y/N) | If Y, separate list ⁴ |
|---------------------|--------------------------------------|-----------------------------|-----------------------|----------------------------------|

Cont'd

| | | | | | | |
|---------------------------|----------------------------------|---------------------------|----------------------------------|---------------------------|----------------------------------|------------------------------|
| Type 1 insulin used (Y/N) | If Y, total daily dose of Type 1 | Type 2 insulin used (Y/N) | If Y, total daily dose of Type 2 | Type 3 insulin used (Y/N) | If Y, total daily dose of Type 3 | CSII used (Y/N) ⁵ |
|---------------------------|----------------------------------|---------------------------|----------------------------------|---------------------------|----------------------------------|------------------------------|

Cont'd

| | | | | | | | | |
|-----------------|-----------------|---------------------|--------------|----|----------------|---------------------|----------------------------------|--|
| Sbp at Visit -2 | Dbp at Visit -2 | Heart rate Visit -2 | T°C Visit -2 | Ht | Wt at Visit -2 | ECG performed (Y/N) | If N, separate list ⁶ | If Y, (normal / abnormal, not sig/ abnormal and sig) |
|-----------------|-----------------|---------------------|--------------|----|----------------|---------------------|----------------------------------|--|

Cont'd

| | | | | | |
|----------------------------|--------------------------------|----------------------------------|---|------------------------------------|----------------------------------|
| Phy exam at Visit -2 (Y/N) | If N, list reason ⁷ | If Y, Any system abnormal? (Y/N) | If abnormal, separate list ⁸ | Abnormality, clinically sig? (Y/N) | If Y, separate list ⁹ |
|----------------------------|--------------------------------|----------------------------------|---|------------------------------------|----------------------------------|

Cont'd

| | | | | | |
|--------------------------------|-----------------|-----------------|---------------------|--------------|----------------|
| Date of assessment at Visit -1 | Sbp at Visit -1 | Dbp at Visit -1 | Heart rate Visit -1 | T°C Visit -1 | Wt at Visit -1 |
|--------------------------------|-----------------|-----------------|---------------------|--------------|----------------|

¹List ongoing medical problems for each subject in a separate spreadsheet. ²List smoking details as captured in CRF for each current smoker in a separate spreadsheet. ³List smoking details as captured in CRF for each former smoker in a separate spreadsheet. ⁴List alcohol consumption details as captured in CRF for each drinker. ⁵List CSII details as captured in CRF for each CRF user. ⁶List reason for not performing ECG for each subject in a separate spreadsheet. ⁷List reasons for not completing physical examination for each non-completer in a separate spreadsheet. ⁸List all information about the abnormalities for each subject as captured in CRF in a separate spreadsheet. ⁹List all clinically significant abnormalities as captured in CRF in a separate spreadsheet.

- Description of baseline characteristics (laboratory assays)

Table 3 shows the headings of the data file to describe baseline characteristics with laboratory assays

| | | | | | | | |
|--------------|-----------|----------|-------------------|------------|-----------|------|----------------------|
| Screening No | Centre No | Visit No | HbA1c at Visit -1 | Serum Aabs | DRB1*0401 | A*02 | Pregnancy test (Y/N) |
|--------------|-----------|----------|-------------------|------------|-----------|------|----------------------|

Cont'd

| | | | |
|-----------------|--------------------------|----------------------|-----------------------|
| Urine C peptide | Albumin/creatinine ratio | Beta 2 microglobulin | Insulin cell free DNA |
|-----------------|--------------------------|----------------------|-----------------------|

KCL

- Table 4 shows the headings of the data file for assessing adherence to study intervention

| | | | | | | | |
|--------------|-----------|---------------|---------------|---------------|--------------|--------------|--------------|
| Screening No | Centre No | Visit 1 date* | Visit 2 date* | Visit 3 date* | Visit 4 date | Visit 5 date | Visit 6 date |
|--------------|-----------|---------------|---------------|---------------|--------------|--------------|--------------|

*Please flag up withdrawn patients or patients with treatment received date different from the visit date

- Endpoints Analysis (clinical observations)

Table 5 shows the headings of the data file for endpoints assessment with clinical observations

| | | | | | | | | |
|--------------|-----------|----------|-------|--------------|--------------|---------------------|--------------|----|
| Screening No | Centre No | Visit No | Rx No | Sbp (pre-Rx) | Dbp (pre-Rx) | Heart rate (pre-Rx) | T°C (pre-Rx) | Wt |
|--------------|-----------|----------|-------|--------------|--------------|---------------------|--------------|----|

Cont'd

| | | | | | | |
|---------------------|----------------------------------|--|--------------------------|--------------------------------|-----------------------------------|---|
| ECG performed (Y/N) | If N, separate list ¹ | If Y, (normal / abnormal, not sig/ abnormal and sig) | Phy exam performed (Y/N) | If N, list reason ² | If Y, Any system abnormal ? (Y/N) | If abnormal, separate list ³ |
|---------------------|----------------------------------|--|--------------------------|--------------------------------|-----------------------------------|---|

Cont'd

| | | | | | | |
|------------------------------------|----------------------------------|-------------------------|-----------------------|-----------------|-----------------|-----------------|
| Abnormality, clinically sig? (Y/N) | If Y, separate list ⁴ | Capillary blood glucose | Taking insulin? (Y/N) | If Y, TDD Day 1 | If Y, TDD Day 2 | If Y, TDD Day 3 |
|------------------------------------|----------------------------------|-------------------------|-----------------------|-----------------|-----------------|-----------------|

Cont'd

| | | | | | | |
|-----------------------------|----------------------------------|-------------------------------|----------------------------------|-------------------------------|-----------------------|-------------------|
| Any change in insulin (Y/N) | IF Y, separate list ⁵ | Concomitant medication? (Y/N) | If Y, separate list ⁶ | Injection per scheduled (Y/N) | If N, delayed /missed | Reason as per CRF |
|-----------------------------|----------------------------------|-------------------------------|----------------------------------|-------------------------------|-----------------------|-------------------|

Cont'd

| | | | | | | |
|----------|--------------------|-----------------------|--------------------------|-------------------------|----------|----------|
| Batch no | Correct drug (Y/N) | Correct patient (Y/N) | Within expiry date (Y/N) | Adm intradermally (Y/N) | Date adm | Time adm |
|----------|--------------------|-----------------------|--------------------------|-------------------------|----------|----------|

Cont'd

| | | | | | | |
|------------|---------------|----------------|---------------------|----------------------------------|--------------------------------------|---|
| Site (L/R) | Pain (needle) | Pain (vaccine) | Skin Reaction (Y/N) | IF Y, separate list ⁷ | Post-injection vital signs abnormal? | If abnormal, separate list ⁸ |
|------------|---------------|----------------|---------------------|----------------------------------|--------------------------------------|---|

¹List reason for not performing ECG by subject and visit no in a separate spreadsheet. ²List reasons for not completing physical examination by subject and visit no in a separate spreadsheet. ³List all information about the abnormalities as captured in CRF by patient and visit no in a separate spreadsheet. ⁴List all clinically significant abnormalities as captured in CRF by patient and visit no in a separate spreadsheet. ⁵List changes in insulin as captured in the change of insulin log by patient in a separate spreadsheet. ⁶List concomitant medications as captured in concomitant medication log by patient in a separate spreadsheet. ⁷List reaction details as captured in post injection skin reaction log by patient and visit no in a separate spreadsheet. ⁸List whether the observation was judged to be clinically significant and whether it is an AE.

- Endpoints Analysis (laboratory assays)

Table 6 shows the headings of the data file for endpoints assessment with laboratory assays

For each of the analytes: eg GAD65

| | | | | |
|--------------|-----------|--------------|----------|----------|
| Screening No | Centre No | Treatment No | Visit -2 | Visit -1 |
|--------------|-----------|--------------|----------|----------|

Cont'd

| | | | | | |
|---------|---------|---------|---------|---------|---------|
| Visit 1 | Visit 2 | Visit 3 | Visit 4 | Visit 5 | Visit 6 |
|---------|---------|---------|---------|---------|---------|

For a full list of all the analytes, please refer to the Data Transferral Plan in Section 10 of the Data Management Plan

- Questionnaire Data

Table 7 shows the headings of the data file for endpoints assessment with questionnaire data

At Visit 1

| | | | | | | |
|--------------|-----------|----------|-------|------------|---------------|--------------|
| Screening No | Centre No | Visit No | Rx No | HFS items* | ADDQoL items* | DTSQs items* |
|--------------|-----------|----------|-------|------------|---------------|--------------|

Multiple columns

At Visit 5

| | | | | | | | |
|--------------|-----------|----------|-------|------------|---------------|--------------|--------------|
| Screening No | Centre No | Visit No | Rx No | HFS items* | ADDQoL items* | DTSQs items* | DTSQc items* |
|--------------|-----------|----------|-------|------------|---------------|--------------|--------------|

Multiple columns

- Safety data

Table 8 shows the headings of the data file for AE assessment

| | | | | | | | |
|--------------|-----------|-------|-------|------------|----------|-----------------------|---------------------------|
| Screening No | Centre No | Rx No | AE no | Start date | End date | Serious? 1=Y / 2=N | If Y, print full SAE form |
|--------------|-----------|-------|-------|------------|----------|-----------------------|---------------------------|

Cont'd

| | | | |
|---|--|---|---|
| Severity 0=no AE, 1=mild, 2=moderate,3=severe | Study drug action 0=none 1=temp interrupt 2=permanently withdraw | Outcome 0=resolved 1=resolved with sequela 2=not resolved | Relationship to study drug 0=not related 1=unlikely 2=possibly 3=probably 4=very likely |
|---|--|---|---|

Table 9 shows the headings of the data file for safety blood test reporting

| | | | | | | |
|--------------|-----------|----------|-------------------------|---------------------------|------------------|------------------|
| Screening No | Centre No | Visit No | Hb (Males) Normal (Y/N) | Hb (Females) Normal (Y/N) | Hct Normal (Y/N) | MCV Normal (Y/N) |
|--------------|-----------|----------|-------------------------|---------------------------|------------------|------------------|

Cont'd

| | | | | | | |
|------------------|------------------|------------------|------------------------|--------------------------|------------------------|--------------------------|
| MCH Normal (Y/N) | WBC Normal (Y/N) | RBC Normal (Y/N) | Platelets Normal (Y/N) | Neutrophils Normal (Y/N) | Basophils Normal (Y/N) | Eosinophils Normal (Y/N) |
|------------------|------------------|------------------|------------------------|--------------------------|------------------------|--------------------------|

Cont'd

| | | | | | | |
|-------------------------------|--------------------|----------------------|-------------------------|------------------------|-------------------|---------------------|
| Prothrombin Time Normal (Y/N) | HbA1c Normal (Y/N) | Glucose Normal (Y/N) | Creatinine Normal (Y/N) | Potassium Normal (Y/N) | Urea Normal (Y/N) | Sodium Normal (Y/N) |
|-------------------------------|--------------------|----------------------|-------------------------|------------------------|-------------------|---------------------|

Cont'd

| | | | | | | |
|----------------------|------------------------|------------------------|-----------------------------------|----------------------------|----------------------|------------------------------|
| Calcium Normal (Y/N) | Phosphate Normal (Y/N) | Magnesium Normal (Y/N) | Alkaline Phosphatase Normal (Y/N) | Total Protein Normal (Y/N) | Albumin Normal (Y/N) | Total Bilirubin Normal (Y/N) |
|----------------------|------------------------|------------------------|-----------------------------------|----------------------------|----------------------|------------------------------|

Cont'd

| | | | | | | |
|-------------------------|-------------------------|------------------|--------------------------------|-------------------|-------------------|----------------------------|
| AST (SGOT) Normal (Y/N) | ALT (SGPT) Normal (Y/N) | TSH Normal (Y/N) | Total Cholesterol Normal (Y/N) | HDLC Normal (Y/N) | LDLC Normal (Y/N) | Triglycerides Normal (Y/N) |
|-------------------------|-------------------------|------------------|--------------------------------|-------------------|-------------------|----------------------------|

Cont'd

| | | |
|------------------|------------------|------------------|
| IgA Normal (Y/N) | IgM Normal (Y/N) | IgG Normal (Y/N) |
|------------------|------------------|------------------|

List details as captured in CRF for parameter not within the normal range for the patient, visit and parameter concerned

Table 10 shows the headings of the data file for safety urine test reporting

| | | | | | |
|--------------|-----------|----------|------------------------|-----------------------|-----------------------------|
| Screening No | Centre No | Visit No | PH Blood Normal (Y/N)* | Protein Normal (Y/N)* | Pregnancy test (+ve, -ve)** |
|--------------|-----------|----------|------------------------|-----------------------|-----------------------------|

* List details as captured in CRF for parameter not within the normal range for the patient, visit and parameter concerned

**Please flag patients with positive pregnancy test
